8.1.1 Prostate-specific Antigen (PSA) Response and Progression (mCRPC only)

Blood for PSA assessment will be collected during Screening, on Day 1 of Cycles 1 to 5, every second cycle thereafter (i.e., Cycles 7, 9, 11 etc.), at the EOT/ED Visit and at the 6-, 9- and 12-month Follow-up Visits for all patients including those who discontinue the study for any reason other than disease progression (Table 1-1 [Parts 1 and 2]). Patients who discontinue the study drug for reasons other than disease progression will continue to have PSA evaluated until disease progression, withdrawal of consent, initiation of new anticancer therapy, the end of the 12-month follow-up period or death, whichever comes first. Patients who discontinue the study

drug due to disease progression do not need to provide PSA samples during the Follow-up Visits. PSA will be used as a blood-based biomarker for tracking and monitoring the response state during the study for mCRPC.

A PSA response will be considered as a PSA value reduction $\ge 30\%$ from baseline at the end of Cycles 3 and 6. A PSA response reduction from baseline at any time point will also be assessed as a secondary objective.

According to PCWG-3, a sequence of rising PSA values should be obtained at a minimum of 1-week intervals with a starting value of 2.0 ng/mL. PSA PFS is the time from first dose administration to PSA progression or death.

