8.1.2 Disease Control Rate

Disease control rate is measured by the percentage of patients with a best overall confirmed response of CR or PR at any time plus SD from first dose administration until disease progression or death due to any cause or the start of new anticancer therapy. CR, PR plus SD will be assessed based on RECIST v1.1 (Table 1-1 [Parts 1 and 2]).

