8.1.3 Tumor Imaging Assessment

In this study, the preferred assessment of soft tissue lesions is CT or MRI scans using RECIST v1.1 criteria and the preferred assessment method for bone lesions is bone scan using PCWG-3.

Tumor imaging using RECIST v1.1 and PCWG-3 criteria will be performed during within 28 days prior to enrollment, every 8 weeks (\pm 7 days) from the first study dose administration up to Week 26, and every 12 weeks (\pm 7 days) thereafter until disease progression (as defined by RECIST v1.1 and PCWG-3 criteria), withdrawal of consent, initiation of new anticancer therapy or death. Tumor imaging should ideally be performed during the rest period before the start of the next treatment cycle.

- If a patient permanently discontinues the study drug due to disease progression according to RECIST v1.1 criteria, a tumor imaging and disease response assessment is not required.
- If a patient permanently discontinues the study drug due to clinical disease progression, a tumor imaging and disease response assessment does not need to be repeated if completed ≤ 28 days after the last dose of study drug.

For patients who permanently discontinue study drug for any reason other than confirmed disease progression, tumor imaging and disease response assessments will continue to be

performed every 12 weeks (\pm 7 days) for up to 12 months after the last dose of the study drug until disease progression, withdrawal of consent, initiation of new anticancer therapy, the patient is lost to follow-up or death, whichever comes first.

- If a patient meets disease progression during the follow-up period according to RECIST v1.1 criteria, a tumor imaging and disease response assessment is not required.
- If a patient meets clinical disease progression during the follow-up period, a tumor imaging and disease response assessment does not need to be repeated if completed ≤ 28 days after the date of clinical disease progression.

For patients who permanently discontinue the study drug or the follow-up period due to withdrawal of consent, the Investigator is to obtain tumor imaging and conduct a disease assessment at the time of the ED Visit or final Follow-up Visit if the patient agrees. A tumor imaging and disease response assessment does not need to be repeated if completed ≤ 28 days of the date of withdrawal of consent.

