8.1.7 Skeletal-related Events and Symptomatic Skeletal Events Assessment

Skeletal-related events and SSEs will be evaluated based on the patient's clinical history and examinations, including but not limited to incidence of fractures and pain. Assessments will be performed at each on-site study visit.

8.1.8 **Progression-free Survival**

Progression-free survival is defined as the duration of time from first dose administration to date of disease progression is objectively documented, including tumor progression, early discontinuation or death prior to data cut-off. Patients alive and progression-free at the time of data cut-off will be censored at the date last known alive. Progression-free survival will be assessed every 8 weeks (\pm 7 days) from the first dose administration up to Week 26, and every 12 weeks (\pm 7 days) thereafter until disease progression according to RECIST v1.1 criteria.

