8.1.10 Overall or Objective Response Rate

Response rate is defined as the proportion of patients who have confirmed CR or PR by objective disease progression RECIST v1.1, as assessed by the Investigator/local radiologist. Overall or ORR will be assessed every 8 weeks (\pm 7 days) from the first dose administration up to Week 26, and every 12 weeks (\pm 7 days) thereafter until disease progression.

Complete response is defined when all target lesions present at baseline have disappeared (with the exception of lymph nodes which must be < 10 mm to be considered nonpathological) and no new lesions have developed since baseline. A visit response of PR is defined when the sum of diameters of the target lesions has decreased by 30% or more compared to baseline (with no evidence of progression).

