9.4 Statistical Analyses

The statistical analysis plan (SAP) will be developed and finalized prior to database lock. Below is a description of planned statistical analyses. Further details are presented in the SAP.

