9.4.7.2 Efficacy of NOX66

The following efficacy analysis will be conducted for the patients enrolled to Part 1 and Part 2 of the study. All analyses are based on the FAS. Results will be summarized by dose cohort (Part 1) or treatment arm (Part 2).

For patients with mCRPC, the change in PSA from baseline will be summarized by dose cohort (Part 1) or treatment arm (Part 2, Arm 1) assessed using samples collected on Day 1 of Cycles 1 to 5, every second cycle thereafter (i.e., Cycles 7, 9, 11 etc.), at the EOT/ED Visit and at the 6-, 9- and 12-month Follow-up visits for all patients including those that discontinued for any reason other than disease progression. A PSA response will be considered as a PSA value reduction \geq 30% from baseline at the end of Cycles 3 and 6. A PSA reduction from baseline at any time point will also be assessed as a secondary objective.

Overall response rate, defined as the percentage of patients with CR and PR, will be assessed based on change from baseline imaging (RECIST v1.1 and PCWG-3 criteria for measurable or evaluable lesions). The number and proportion of responders (CR and PR) will be presented along with the exact 95% CI (Clopper-Pearson) for the time points after Day 1. Patients are allowed to continue study treatment until disease progression, unacceptable toxicity, withdrawal of consent, start of a new anticancer therapy, withdrawal of the patient by the Investigator or termination of the study by Sponsor. Tumor imaging assessment will be continued as scheduled for the patients who are discontinued from the study for reasons other than disease progression (see Section 8.1.3). The best overall response (CR, PR, SD or progression) will be summarized.

The change in ECOG from baseline will be summarized by dose cohort (Part 1) or treatment arm (Part 2) over time. The change in pain severity and pain interference with daily activities from baseline will be summarized by dose cohort (Part 1) or treatment arm (Part 2) over time. The number and proportion of patients with a pain response (\geq 2-point reduction in pain severity and no additional opioid use) will be summarized over time along with the exact 95% CIs

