(Clopper-Pearson). The time to morphine administration and/or use of analgesics together with change from baseline assessment will be calculated and summarized by dose cohort (Part 1) and treatment arm (Part 2). The number and proportion of patients with SREs and/or SSEs will be summarized at each time point and presented along with the exact 95% CI (Clopper-Pearson).

Quality of Life analyses will be performed for the Safety Analysis Set. Scale measures from the EORTC-QLQ-C30, BPI-SF, PEQ, and FACT-P (mCRPC patients only) will be summarized for all patients by dose at each on-site visit as well as the change from baseline to each on-site visit.

Survival functions will be computed for OS, PFS and PSA reduction/progression (for Part 2, Arm 1 only) using the Kaplan-Meier method. Estimates of median survival times will be presented by dose cohort (Part 1) or treatment arm (Part 2) along with 2-sided 95% CIs. The 25th and 75th percentiles and the range (minimum, maximum) will be presented as well.

Duration of response is defined as the time from the first documented overall response of CR, PR or SD to the first documented overall response of progressive disease. This will be estimated using the Kaplan-Meier method. Estimates of median survival times will be presented along with the two-sided 95% CI. The 25th and 75th percentiles and range (minimum, maximum) will also be presented.

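### Duration of response starts at the first CR, PR or SD, although responders are CR and PR only, so its median does not measure how long responses last

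*Combined protocol and SAP*

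**What the plan says.** - **Definition of DOR.** Section 9.4.7.2 and the efficacy part of the synopsis use the same wording: the "time from the first documented overall response of CR, PR or SD to the first documented overall response of progressive disease". It is estimated by Kaplan-Meier, with a median, two-sided 95% CI, quartiles and range.
- **Who is a responder.** Earlier in section 9.4.7.2, the overall response rate is the percentage with CR and PR, and "The number and proportion of responders (CR and PR) will be presented". Section 8.1.10 says: "Response rate is defined as the proportion of patients who have confirmed CR or PR".
- **Where SD counts.** Section 8.1.2 places it in the disease control rate: "best overall confirmed response of CR or PR at any time plus SD".
- **Population.** Table 3-1 and the synopsis table limit DOR to patients with measurable disease. Neither limits it to responders.
- **End of the interval.** DOR ends only at progressive disease. By contrast, section 8.1.8 includes "early discontinuation or death prior to data cut-off" in PFS, and section 8.1.1 states: "PSA PFS is the time from first dose administration to PSA progression or death".
- **Other detail.** Section 9.4 says: "Further details are presented in the SAP". The file reviewed contains no separate SAP text.

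**The concern.** SD is not a response when responders are counted, but it is one when response is timed. This has two effects. Patients who never respond enter the DOR curve, and patients who respond after a period of SD are timed from a scan that precedes their response. A reader of the study report would take a median labelled duration of response as the durability of CRs and PRs. The figure produced would be closer to a duration of disease control.

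A second, conditional matter is that death is not named as an end of the interval. How deaths without documented progression are handled is left open.

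**Working it through.** The plan gives no expected median, event count or precision for DOR, so there is no figure to reproduce. The check compares definitions and uses a little arithmetic for scale.

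**1. Apply the definition to each pattern of scans (measurable disease).**

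| Scan sequence | DOR as written | DOR from first CR/PR |
|---|---|---|
| PR at first scan, later PD | starts at first scan | the same |
| SD, then PR, then PD | starts at the SD scan | starts at the PR scan |
| SD only, then PD | enters, starts at the SD scan | does not enter |
| PD at first scan | does not enter | does not enter |

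The second and third rows are affected. Nothing in the documents removes the SD-only patients.

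**2. How early the clock starts for SD-then-PR patients.** Section 8.1.3 schedules imaging every 8 weeks "from the first study dose administration up to Week 26, and every 12 weeks" thereafter. Nominal scans are at Weeks 8, 16 and 24.
- Gaps up to Week 24: 16 − 8 = 8 weeks and 24 − 16 = 8 weeks. With SD at Weeks 8 and 16 and PR at Week 24, the clock starts 24 − 8 = 16 weeks early.
- Next scan: 24 + 12 = Week 36 or 26 + 12 = Week 38, because the section does not say where the 12-week count begins. The gap is 36 − 24 = 12 or 38 − 24 = 14 weeks. Later gaps are 12 weeks.

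These are nominal values, not bounds. Each scan has a ±7 day window, and imaging at an early discontinuation visit can fall off schedule.

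**3. What the written quantity approximates.** For an on-schedule patient with CR, PR or SD at Week 8, DOR as written equals time to progression from first dose minus 8 weeks. It is a shifted time to progression among patients not progressing at the first scan.

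**4. Illustration of the mix (section 2.1, study NOX66-002A at 3 months).** There were 1 + 2 = 3 patients with PR and 14 with SD, so 3 + 14 = 17 had disease control, and 14/17 = 82% of them had SD. This is status at one time point in an earlier mCRPC study. It does not count patients who were only ever SD, and it is not a forecast for this study.

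**5. Direction.** Suppose, purely as an assumption, exponential durations with median mR in responders and mS in SD-only patients, and an SD share w = 14/17. The pooled median t solves (1 − w)·2^(−t/mR) + w·2^(−t/mS) = 0.5.
- mR = 9, mS = 4 months: t = 4.5, below the responders' 9.
- mR = 6, mS = 9 months: t = 8.4 (8.35 before rounding), above the responders' 6.

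None of these medians is in the documents. The example shows only that the shift can go either way.

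**6. Deaths.** If deaths without documented progression are censored instead of counted as events, the Kaplan-Meier curve loses downward steps. It therefore lies at or above the curve that counts them, and the median is later or unchanged. With no such deaths, nothing changes.

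**The case against.** **The phrase may be assessment language.** Section 9.4.7.2 also lists SD among the categories of best overall response, so an overall response of SD can be read as a scan category, not as a claim that SD patients responded. That may explain how SD came in. It does not change who enters the curve, or the label on the median.

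**The definition is explicit, and other endpoints are reported.** A reader who looks it up can see that SD is included, and response rate, best overall response and PFS are given separately. This limits the harm, but the mismatch with the responder definition in the same section remains.

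**The SAP may settle it.** For deaths and censoring this stands: the protocol text is silent and the SAP is not in the file. For SD it does not, because the protocol gives a definite rule that an SAP faithful to it would carry forward.

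**The numbers are thin.** This stands. The 14 of 17 cannot be scaled to this study. In Part 2 a measurable lesion is required only for BC and NSCLC patients, so the number of Arm 1 patients eligible for DOR is unknown. The number of SD-then-PR patients is unknown too.

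**Stronger readings that a reader might infer.** One is that the median will be inflated; step 5 shows that the documents do not fix the direction. Another is that censored deaths will lengthen it. That requires an SAP that does not count deaths as events and censors them, and even then the median may be unchanged.

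**Conclusion.** The definition is wrong as written. Under it, patients whose best result is SD enter the DOR curve, and SD-then-PR patients are timed from before their response, by a nominal 8 weeks per scan interval up to Week 24. The median would not measure how long responses last. This rests on the text alone and is firm.

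The direction and size of the distortion cannot be determined from the documents. The point about deaths is conditional: if the SAP does not add death as an event and such deaths are censored, the median is lengthened or unchanged.

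The weight is moderate. DOR is a descriptive secondary endpoint, section 9.1 plans no hypothesis tests, and no decision rule uses DOR. It would be a mistake to infer any effect on the primary endpoints or the sample size.

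**What to change.** In section 9.4.7.2 and the synopsis, carried into the SAP:

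- Define DOR as the time from first documented CR or PR to the earlier of first documented progression and death from any cause, in CR/PR patients with measurable disease.
- Use the same confirmation rule as the response rate, and say which it is. Section 8.1.10 requires confirmation; section 9.4.7.2 does not mention it.
- State the censoring rule.
- Note that the response rate in section 9.4.7.2 also covers evaluable lesions, so some counted responders may have no DOR.

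If the CR/PR/SD quantity is wanted, report it separately, labelled duration of disease control. If it is measured from first dose in patients selected for disease control, say that it includes guaranteed event-free time up to the first scan (nominally Week 8) and is close to PFS in a selected group.

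The cost is wording and programming, with no new data, visits or patients. The downside is that few responders may contribute, so the estimate would be imprecise and the median may not be estimable.

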Evaluate the preliminary clinical efficacy of NOX66 plus low-dose EBRT in patients with mCRPC and other solid tumors	 Preliminary clinical efficacy as determined by: Change from baseline in PSA (mCRPC only) at any time point. Overall response rate assessed by RECIST v1.1 criteria (all tumor types) and PCWG-3 criteria (mCRPC). Duration of response (for patients with measurable disease). Change from baseline ECOG scores. Change from baseline in tumor size and number. PFS and OS.
Explore the effects of NOX66 on pain and other cancer-related signs and symptoms	 Effects on pain and other cancer-related signs and symptoms as determined by: Change from baseline in pain scores based on the BPI-SF questionnaire. SREs and SSEs. Change of dose and frequency of morphine administration and analgesic use.

Objectives	Endpoints				
Evaluate the QoL using PRO questionnaires	 QoL as assessed by: Change from baseline in PEQ. Change from baseline in EORTC-QLQ-C30. Change from baseline in FACT-P (mCRPC only). 				
Exploratory Objectives and Endpoints					
Characterize the relationship between pharmacodynamic biomarkers and idronoxil plasma concentrations (if a meaningful change is observed)	 Change in biomarkers (cytokines, chemokines and ctDNA) from baseline. Change in lipid profile from baseline. 				

AE = adverse event; BC = breast cancer; BPI-SF = Brief Pain Inventory – Short Form; CR = complete response; ctDNA = circulatory tumor deoxyribonucleic acid; DCR = disease control rate; DLT = dose-limiting toxicity; EBRT = external beam radiotherapy; ECG = electrocardiogram; ECOG = Eastern Cooperative Oncology Group; EORTC-QLQ-C30 = European Organisation for Research and Treatment of Cancer Quality of Life Questionnaire for Cancer Patients; FACT-P = Functional Assessment of Cancer Therapy – Prostate; mCRPC = metastatic castration-resistant prostate cancer; MTD = maximum tolerated dose; NSCLC = non-small-cell lung cancer; OS = overall survival; PCWG-3 = Prostate Cancer Working Group 3; PEQ = Patient Experience Questionnaire; PFS = progression-free survival; PK = pharmacokinetic(s); PR = partial response; PRO = Patient Reported Outcome; PSA = prostate-specific antigen; QoL = quality of life; RECIST = Response Evaluation Criteria in Solid Tumors; RP2D = recommended Phase 2 dose; SD = stable disease; SRE = skeletal-related events; SSE = symptomatic skeletal events; TEAE = treatment-emergent adverse event

4 Study Design

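### Duration of response ends only at documented progression, so a patient who dies without it can never be an event, unlike in PFS and PSA PFS

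*Combined protocol and SAP*

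**What the plan says.** Section 9.4.7.2 starts the clock for duration of response at the earliest recorded CR, PR or SD and runs it "to the first documented overall response of progressive disease. This will be estimated using the Kaplan-Meier method". The synopsis gives the same definition. Table 3-1 lists it as a secondary endpoint for patients with measurable disease. Neither definition mentions death, and no censoring rule is given for this endpoint.

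The plan's two other progression-based time-to-event measures do mention death:

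- **PFS (8.1.8)** runs to objectively documented progression, "including tumor progression, early discontinuation or death prior to data cut-off". It has a censoring rule: "Patients alive and progression-free at the time of data cut-off will be censored at the date last known alive".
- **PSA PFS (8.1.1):** "PSA PFS is the time from first dose administration to PSA progression or death".

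On imaging, section 8.1.3 schedules scans every 8 weeks (± 7 days) to Week 26 and every 12 weeks after that. It also has an exemption, which begins "If a patient permanently discontinues the study drug due to clinical disease progression, a tumor imaging and disease response assessment does not need to be"; in substance, no further scan is required when one falls within a 28-day window around the last dose. Section 9.4 leaves further analysis detail to the SAP.

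**The concern.** A patient whose response or stable disease ends in death, with no scan showing progression first, has no event under this definition. Kaplan-Meier then needs some other handling for that patient. The usual one, censoring, treats the patient as if the response might have continued. The duration then looks longer than the time patients spent alive and free of documented progression. It is also no longer comparable with PFS in the same report.

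Such deaths are plausible here. Patients have metastatic disease, have failed at least one prior line and may have ECOG status 2, and scans are 8 or 12 weeks apart. Because the clock also starts at SD (a separate matter), many patients enter the analysis. In the previous study in mCRPC, 17 of 19 evaluable patients had disease control at 3 months, 14 of them with SD (section 2.1).

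**Working it through.** The plan gives no median, event count or death rate for this endpoint, so there is no figure of its own to reproduce.

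**1. A case under the protocol's schedule.** Response is seen at the Week 16 scan, drug is stopped for clinical progression at Week 18 without a new scan, and the patient dies at Week 22.

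- The Week 16 scan is about 14 days before the stop, inside the 28-day window as the Schedule of Activities notes word it (section 8.1.3 counts from after the last dose).
- The next 8-weekly scan would be Week 24 ± 1, so no earlier than Week 23. A 12-weekly follow-up scan would fall near Week 18 + 12 = Week 30. Both come after the death.
- Duration of response therefore has no event. PFS has one: at death, or earlier, because 8.1.8 also lists early discontinuation.

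The exemption is not essential. A patient still on drug who dies at Week 22 also dies before the next scheduled scan.

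**2. Direction.** Let n be the number at risk at an event time, d the progressions and m the deaths without progression. With deaths censored at the date of death, the Kaplan-Meier factor is 1 - d/n. With deaths as events it is 1 - (d + m)/n, which is never larger. So the censored curve cannot lie below the progression-or-death curve. It lies above it from the first such death until both reach zero.

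**3. Size under a constant hazard (q assumed).** Let h be the total hazard and q the share of first events that are deaths without documented progression. The true median is ln2/h. With deaths censored it is ln2/((1-q)h). The ratio is 1/(1-q).

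| q (assumed) | Ratio |
|---|---|
| 5% | 1/0.95 = 1.05 |
| 10% | 1/0.90 = 1.11 |
| 20% | 1/0.80 = 1.25 |
| 30% | 1/0.70 = 1.43 |

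**4. Size on the scan grid.** A simulation of 200,000 patients used scans 8-weekly to Week 26 and then 12-weekly, with disease control first seen at Week 8 and assumed exponential times to progression and death. Mean duration restricted to 52 weeks, in weeks:

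| Latent progression median | Deaths first | Progression or death | Deaths censored | Ratio |
|---|---|---|---|---|
| 16 weeks | 6% | 24.3 | 25.3 | 1.04 |
| 16 weeks | 12% | 23.3 | 25.3 | 1.09 |
| 16 weeks | 24% | 21.1 | 25.4 | 1.20 |
| 16 weeks | 37% | 18.7 | 25.3 | 1.35 |
| 24 weeks | 6% | 30.1 | 31.0 | 1.03 |
| 24 weeks | 35% | 24.5 | 31.0 | 1.27 |

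Censoring at the last scan instead of at death gave the same results. Excluding these patients also overstated the mean, by less: 22.1 against 21.1 weeks at 24% deaths.

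Medians moved unevenly. With a 24-week latent median they were 28.0 under both rules at 6% deaths, but 18.4 against 28.0 at 35%. With a 16-week latent median they were 16 under both rules at 6%, 12% and 37%, and 16 against 28 at 24%. That last jump is fragile, because the progression-only curve there stands at exp(-ln2 × 16/16) = 0.50 exactly.

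**5. A ten-patient illustration (invented data).** Progression at 8, 16, 16, 28, 28, 40 and 52 weeks of duration; death without progression at 8, 12 and 20.

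- Progression or death: 8/10 = 0.80 at 8 weeks, 0.70 at 12, 5/10 = 0.50 at 16. The curve first reaches 0.5 at 16 weeks.
- Deaths censored: 9/10 = 0.90 at 8 weeks; 0.90 × 5/7 = 0.643 at 16; 0.643 × 2/4 = 0.321 at 28. The curve first reaches 0.5 at 28 weeks.

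Three deaths in ten move this median by a full 12-week interval, 28/16 = 1.75, against 1.43 from the smooth formula.

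**The case against.** The best reply is that the plan never says deaths are censored. It is silent, and section 9.4 defers detail to an SAP that could add a rule. That stands as far as it goes: a reader might infer that the plan prescribes censoring at death, and it does not. But the omission of death from the event definition is explicit. A censoring rule added later would not make death an event without changing that definition. Exclusion, the other handling examined, also lengthened the estimate in the simulation.

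Several stronger readings do not hold:

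- **PFS as a clean benchmark.** A reader might attribute any gap between the two measures to deaths. Section 8.1.8 also lists early discontinuation as an ending, so the gap can have other causes.
- **Disease control rate as a further inconsistency.** Section 8.1.2 closes its window at death, but that window is for counting best response in a proportion. It is not a time-to-event definition.
- **The imaging exemption as a wide gap.** It covers only a short period. A Week 8 scan (Week 9 at the latest) is at least 35 days before a stop at Week 14, so it would not excuse a new scan.
- **A fixed inflation in months.** A reader might turn the ratios above into a reported median. No document supplies q, and event times on this scan grid are not continuous. Inclusion requires a life expectancy of at least 6 months, which gives no support for the higher values of q.

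The consequence is also limited. The study tests no hypotheses (9.1), OS and PFS are reported alongside, and no sample size or decision rests on this endpoint.

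**Conclusion.** The point holds. As defined, duration of response cannot register a death without documented progression, while PFS and PSA PFS can, and no reason is given for the difference. If such deaths are censored at the date of death, the estimate can only be too long relative to a progression-or-death definition, and it is too long once one such death occurs.

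The direction is firm on that condition; the size is not known. It is zero if no such death occurs. The factors of 1.11 to 1.43 rest on assumed q of 10% to 30% and constant hazards. The simulated ratios of 1.03 to 1.35 rest on assumed progression and death rates. With 40 patients in Arm 1 and 24 to 30 in Arm 2, a few deaths could leave the median where it is or move it by a whole scan interval. This affects the interpretation of a descriptive secondary endpoint only.

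**What to change.** In section 9.4.7.2, the synopsis and the SAP, end duration of response at documented progressive disease or death from any cause, whichever is earlier. Censor patients with neither at their last adequate tumor assessment. State how missed scans, loss to follow-up and the start of new anticancer therapy are handled, since scheduled imaging stops when new therapy begins.

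Reconcile that censoring date with section 8.1.8, which censors PFS at the date last known alive. Otherwise the two measures would share the same events but censor on different dates.

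The cost is one or two sentences in each place. Deaths and scan dates are already collected, so no new data are needed. The downside is that the reported duration may be shorter.
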